#### 5.6.4 Vital Signs

Descriptive statistics for vital signs parameters (ie, systolic and diastolic BP, pulse, respiratory rate, temperature, weight) and changes from baseline will be presented by visit.

In addition, the criteria described in the table below will be used to determine clinically notable results for blood pressure and heart rate. The number (percentage) of subjects with clinically notable results over all scheduled and unscheduled visits will be summarized.

**Table 1: Criteria for Clinically Notablea Vital Signs**

Variable	Criterion Value	Change Relative to Baseline
Systolic BP	$> 180$ mmHg	Increase of $\geq 20$ mmHg
	$< 90$ mmHg	Decrease of $\geq 20$ mmHg
Diastolic BP	$> 105$ mmHg	Increase of $\geq 15$ mmHg
	$< 50$ mmHg	Decrease of $\geq 15$ mmHg
Heart Rate	$> 120$ bpm	Increase of $\geq 15$ bpm
	$< 50$ bpm	Decrease of $\geq 15$ bpm
Weight		Increase of $> 7\%$
		Decrease of $> 7\%$
a: Clinically notable means that a value must have met both the criterion value and satisfied the magnitude of change relative to baseline.		

The criteria in [Table 2](#) will be used to determine abnormal results for blood pressure and heart rate. The number of subjects with abnormal results will be summarized.

**Table 2: Criteria for Abnormal Vital Signs**

Variable	Change Relative to Baseline
Systolic BP	Increase of $\geq 20$ mmHg
	Decrease of $\geq 20$ mmHg
	Increase of $\geq 40$ mmHg
	Decrease of $\geq 40$ mmHg
Diastolic BP	Increase of $\geq 10$ mmHg
	Decrease of $\geq 10$ mmHg
	Increase of $\geq 20$ mmHg
	Decrease of $\geq 20$ mmHg
Pulse	Increase of $\geq 15$ bpm
	Decrease of $\geq 15$ bpm
	Increase of $\geq 30$ bpm
	Decrease of $\geq 30$ bpm

### 5.6.5 Electrocardiograms

ECG parameters (QTcB, QTcF, PR interval, QRS duration and RR interval) and changes from baseline will be presented by visit.

Shift tables will present changes from baseline in ECG interpretation (categorized as normal; abnormal, not clinically significant; and abnormal, clinically significant) to end of treatment.

In addition, the number (percentage) of subjects with at least one post baseline abnormal ECG result in QTc Bazett and QTc Fridericia during the treatment period will be summarized.

Clinically borderline or abnormal ECG results in QTc Bazett and QTc Fridericia will be categorized as follows:

Absolute QTc interval prolongation:

- QTc interval 430-450 ms
- QTc interval  $>450$  ms
- QTc interval  $>500$  ms

Change from baseline in QTc interval:

- QTc interval increases from baseline 30-60 ms
- QTc interval increases from baseline  $>60$  ms

### 5.6.6 Other Safety Analyses

#### **Aldenkamp-Baker Neuropsychological Assessment Schedule (ABNAS)**

The total ABNAS score (defined as the sum of the individual question scores) and sub-scores for fatigue, slowing, memory, concentration, motor-coordination and language (Brooks et al 2001) will be listed and summarized by visit. Changes from baseline ABNAS sub-scores will be summarized.

**Table 3: Definition between each aspect and question**

Aspect	# of items	Range	Item No
fatigue	5	0-15	1, 7, 13, 18, 24
slowing	5	0-15	2, 8, 14, 19, 23
memory	4	0-12	3, 9, 15, 20
concentration	4	0-12	4, 10, 16,21
motor speed	3	0-9	5, 11, 17,
reading (language)	3	0-9	6, 12, 22

#### **Child Behavior Check List (CBCL 1.5/5 and CBCL 6/18)**

The CBCL 1.5/5 measures problems in children (1.5 to 5 years old). To measure problems, 100 ‘problem items’ are rated on a scale to measure their occurrence. Higher scores indicate greater problems, as the scale ranges from 0, indicating ‘not true,’ to 2, indicating ‘often true.’ 67 of the items are then summed into seven syndrome scores (Emotionally Reactive, Anxious/Depressed, Withdrawn, Somatic Complaints, Attention Problems, Aggressive Behavior syndrome and Sleep problems.) The summation of the first four syndrome scores yields the Internalizing Syndrome composite score, and the summation of the next two syndrome scores yields the Externalizing Syndrome composite score. The total problems score is the summation of all 100 item scores. .

The total problems score, the Internalizing Syndromes score, the Externalizing Syndromes score, and each of the seven individual syndrome scores of the CBCL 1.5/5 will be evaluated using summaries of change from baseline (Week 0) by visit.

**Table 4: Definition CBCL 1.5-5 (Refer to link of CBCL/1 1/2-5 and LDS in profiles at website <http://www.aseba.org/forms.html>)**

Syndrome scale	#of items	Range	Items
Emotionally Reactive	9	(0-18)	21,46,51,79,82,83,92,97,99
Anxious/Depressed	8	(0-16)	10,33,37,43,47,68,87,90
Withdrawn	8	(0-16)	2,4,23,62,67,70,71,98
Somatic Complaints	11	(0-22)	1,7,12,19,24,39,45,52,78,86,93
Internalizing	36	(0-72)	sum of 4 previous scores
Attention Problems	5	(0-10)	5,6,56,59,95
Aggressive Behavior syndrome	19	(0-38)	8,15,16,18,20,27,29,35,40,42,44,53,58,66,69,81,85,88,96
Externalizing	24	(0-48)	sum of 2 previous scores
Sleep problems	7	(0-14)	22,38,48,64,74,84,94
Total	100	(0-200)	Sum of all problem items scores

Also the CBCL 6/18 measures competencies and problems in children (6 to 18 years old). To assess competence, sixteen items are scored for each child, with higher scores indicating better competence. The summed scores are grouped into three sub-scores for competence in activities, social realms and school. The total competence score is the summation of all 16 items.

To measure problems, 120 ‘problem items’ are rated on a scale to measure their occurrence. Higher scores indicate greater problems, as the scale ranges from 0, indicating ‘not true,’ to 2, indicating ‘often true.’ 103 of the items are then summed into eight syndrome scores (Anxious/Depressed, Withdrawn/Depressed, Somatic Complaints, Rule-Breaking Behavior, Aggressive Behavior, Social Problems, Thought Problems, and Attention Problems.) The summation of the first three syndrome scores yields the Internalizing Syndrome composite score, and the summation of the next two syndrome scores yields the Externalizing Syndrome composite score. The total problems score is the summation of the two composite scores, the final three syndrome scores, and the 17 ‘problem items’ that were not included in any of the eight syndrome scores.

The total competence score, the three sub-scores for competence, the total problems score, the Internalizing Syndromes score, the Externalizing Syndromes score, and each of the eight individual syndrome scores of the CBCL 6/18 will be evaluated using summaries of change from baseline (Week 0) by visit.

**Table 5: Definition CBCL 6-18 (Refer to link of CBCL/6-18 scored using three different societies in profiles at website : <http://www.aseba.org/forms.html>)****Competency Scores**

Sub-scores	# of Items	Score Range	Items
Activity	6	(0-15)	I.A, B, II.A, B, IV A, B
Social	6	(0-14)	III.A, B, V.1, 2, VI. A, B
School	4	(0-6)	VII. 1, 2,3,4
Total	16	(0-35)	Sum of 3 previous scores

**Syndrome/ Problems Scores**

Syndrome scale	#of items	Score Range	Items
Anxious/Depressed	13	(0-26)	14,29,30,31,32,33,35,45,50,52,71,91,112
Withdrawn/Depressed	8	(0-16)	5,42,65,69,75,102,103,111
Somatic Complaints	11	(0-22)	47,49,51,54,56a,56b,56c,56d,56e,56f,56g
Internalizing	32	(0-64)	sum of 3 previous scores
Rule-Breaking Behavior	17	(0-34)	2,26,28,39,43,63,67,72,73,81,82,90,96,99,101,105,106
Aggressive Behavior	18	(0-36)	3,16,19,20,21,22,23,37,57,68,86,87,88,89,94,95,97,104
Externalizing	35	(0-70)	sum of 2 previous scores
Social Problems	11	(0-22)	11,12,25,27,34,36,38,48,62,64,79
Thought Problems	15	(0-30)	9,18,40,46,58,59,60,66,70,76,83,84,85,92,100
Attention Problems	10	(0-20)	1,4,8,10,13,17,41,61,78,80
Total	120	(0-240)	Sum of all problem items scores

Additionally, both CBCL results for each subject will be converted to a standardized T-score and classified at baseline and at each evaluation as normal, borderline clinical, or clinical, based on the thresholds provided in the CBCL manual. These classifications and their change from baseline will be presented in tables.

**Lafayette Grooved Pegboard Test (LGPT)**

Time taken to perform the Lafayette Grooved Pegboard Test correctly (i.e. inserting 25 pegs for 8 years or older or 10 pegs for under 8 years old for each hand, ranges up to 300 seconds) will be summarized by visit. If the task cannot be completed correctly at 300 seconds, 300 seconds will be recorded.

Total number of pegs correctly placed and total number of pegs dropped will also be summarized separately for each hand by visit.

Total score for each hand (Trites) will be calculated as time to complete the test + total number of pegs dropped + total number of pegs correctly placed.

All summaries will be calculated by each age group (for 8 years or older, for under 8 years old) separately.

### **Growth parameter**

The actual value and change from baseline in growth parameter (height, weight, TSH, fT3, fT4 and IGF-1) will be summarized by visit. Height and weight will be presented using summary statistics for overall percentile and overall z-score.

### **EEG**

EEG parameters will be summarized and listed as appropriate.

### **Columbia Suicide Severity Rating Scale (C-SSRS)**

Scoring of the C-SSRS will be performed as suggested by the C-SSRS Columbia website [http://www.cssrs.columbia.edu/clinical\\_trials.html](http://www.cssrs.columbia.edu/clinical_trials.html).

The following summaries will be presented for the treatment duration (defined as the period from the date of first dose at Core Study up to 28 days after the date of last dose at Extension Phase, inclusive).

- Number (percentage) of subjects with any treatment-emergent report of suicidal behavior, suicidal ideation, and suicidality (suicidal behavior and/or ideation) will be displayed. A treatment-emergent report of suicidal behavior, suicidal ideation, or suicidality is an answer of 'Yes' to any question in the respective category during the treatment duration.
- Shift from baseline to the maximum suicidal ideation severity rating (0=no ideation present to 5=active ideation with plan and intent) in the treatment duration will assess worsening of suicidal ideation. Any score greater than 0 indicates the presence of suicidal ideation while a score of 4 (active suicidal ideation with some intent to act) or 5 (active suicidal ideation with specific plan and intent) can be used to indicate serious suicidal ideation.

Descriptive statistics and changes from baseline will be presented by visit for the suicidal ideation intensity score and the suicidal ideation severity rating (treated as a continuous variable) to assess change in suicidal ideation over time. The suicidal ideation intensity score ranges from 0 to 25 and is the sum of the 5 intensity items.

## 5.7 Exploratory Analyses

The change from baseline in EQ-5D-Y will be summarized by age and disease cohorts, and by the presence or absence of concomitant EIAED, using descriptive statistics.

## 6 INTERIM ANALYSES

An independent data monitoring committee (DMC) will be constructed to monitor the safety data. The responsibilities, membership, and purpose of the DMC, the timing of the meeting(s), and an outline of the plan for review of the safety data will be documented in the DMC Charter.

## 7 CHANGES IN THE PLANNED ANALYSES

There are currently no changes in the planned analyses.

## 8 DEFINITIONS AND CONVENTIONS FOR DATA HANDLING

### 8.1 Efficacy Data Handling

#### 8.1.1 Pre-randomization/baseline efficacy

All diary data prior to first dose date at Core Study will be used in the computation of Pretreatment Phase seizure frequency per 28 days. The baseline value for other efficacy endpoints will be the last non-missing measurement occurring prior to the first dose of the study drug at Core Study.

#### 8.1.2 Treatment Duration for Efficacy Analyses

The date of first dose of the study drug is considered day 1 in the treatment duration.

The first dose date is the study drug start date and the last dose date is study drug end date from the study medication CRF page.

The treatment duration for efficacy variables is defined as follows:

- For diary seizure data: The duration between the day of first dose at Core Study and the last day of study drug at Maintenance Period in Extension Phase, inclusive.
- For non-diary efficacy data: The duration between the day of first dose at Core Study and 7 days after the last day of study drug at Maintenance Period in Extension Phase, inclusive.

For all efficacy analyses, data reported during Core Study and the Maintenance Period in Extension Phase will be analyzed. The diary seizure data during the Follow-up will be listed.

#### 8.1.3 Handling of Replicate Data

For the CGIC and EQ-5D-Y assessment, the last visit within the treatment duration will be used.

## 8.2 Safety Data Handling

### 8.2.1 Baseline Safety

The baseline value for safety endpoints will be the last non-missing measurement occurring prior to the first dose of the study medication at Core Study.

### 8.2.2 Treatment Duration for Safety Variables

The treatment duration for non-AE safety variables is the same as non-diary efficacy analysis in [Section 8.1.2 Treatment Duration for Efficacy Analyses](#). For AEs, the treatment duration is considered to begin on Day 1 at Core Study and ends 14 days after the last dose of Maintenance Period in Extension Phase.

The post-treatment duration is considered to begin on the day after the treatment duration for safety. Since it is not always possible for all study participants to come in for their clinic visits on the exact day specified in the protocol schedule, the visit week of a subject's visit will be based on the actual visit occurring during the treatment duration. These visits will be used to create by visit summaries for laboratory, vital signs, electrocardiograms and other safety analyses data. The end of treatment value is the last non-missing value in the treatment duration.

Any concomitant medication taken within the 14 days after the last dose data will be listed/summarized as part of the concomitant medication listing/table.

AEs for the subject were collected and reported on CRF starting from the time subject signed informed consent to the last visit in the Follow-up following subject's last dose. Serious AEs were collected for 28 days after the last dose.

For summaries of safety by time points, the time points will be relative to date of first dose. For standardized reporting, study day windows relative to the first dose (Day 1) in the study will be applied to determine into which week the data will be mapped. Scheduled, unscheduled, and early withdrawal visits will be mapped to weeks. [Table 6](#) below gives the mapping of relative day ranges to week for non-AE safety variables. If a subject did not have a recorded observation falling within a given range of days in order to be assigned to a week, the subject's data for that week will be regarded as missing for summarization purposes. If there are two or more assessments in the same window then:

- if the window is the baseline assessment, then the latest assessment will be used in the summary tables;
- if the window is the follow-up assessment, then the latest assessment will be used in the summary tables;

If the window is not the baseline or the follow-up assessment, then the assessment closest to the scheduled assessment will be used in the summary tables. Note that if two assessments are equidistant from the scheduled assessment then the last assessment of the two (within the allowable window) will be used.

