9.5.1.5.1 ADVERSE EVENTS AND EVENTS ASSOCIATED WITH SPECIAL SITUATIONS

An AE is any untoward medical occurrence in a patient or clinical investigation subject administered an investigational product (IP). An AE does not necessarily have a causal relationship with the medicinal product. For this study, the study drugs is perampanel.

The criteria for identifying AEs in this study are:

- Any unfavorable and unintended sign (including an abnormal laboratory finding), symptom, or disease temporally associated with the use of an IP, whether or not considered related to the IP (Note: Every sign or symptom should not be listed as a separate AE if the applicable disease [diagnosis] is being reported as an AE)
- Any new disease or exacerbation of an existing disease

- Any deterioration in nonprotocol-required measurements of a laboratory value or other clinical test (eg, ECG or x-ray) that results in symptoms, a change in treatment, or discontinuation of study drug
- Recurrence of an intermittent medical condition (eg, headache) not present pretreatment (Baseline)
- An abnormal laboratory test result should be considered an AE if the identified laboratory abnormality leads to any type of intervention, withdrawal of study drug, or withholding of study drug, whether prescribed in the protocol or not

All AEs observed during the study will be reported on the CRF. All AEs, regardless of relationship to study drug or procedure, should be collected beginning from the time the subject signs the study ICF through the last visit and for 28 days following study drug discontinuation. Subjects who fail screening primarily due to AE(s) must have the AE(s) leading to screen failure reported on the Screening Disposition CRF. SAEs will be collected for 28 days after the last dose.

Abnormal laboratory values should not be listed as separate AEs if they are considered to be part of the clinical syndrome that is being reported as an AE. It is the responsibility of the investigator to review all laboratory findings in all subjects and determine if they constitute an AE. Medical and scientific judgment should be exercised in deciding whether an isolated laboratory abnormality should be classified as an AE. Any laboratory abnormality considered to constitute an AE should be reported on the AE CRF.

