### 8.2.2 Treatment Duration for Safety Analyses

The treatment duration for non-AE safety variables is same of non-diary efficacy analysis in 8.1.2 Treatment Duration for Efficacy Analyses. For AEs, the treatment duration is considered to begin on Day 1 and ends 28 days after the last dose of treatment phase .

The post-treatment duration is considered to begin on the day after the treatment duration for safety. Since it is not always possible for all study participants to come in for their clinic visits on the exact day specified in the protocol schedule, the visit week of a subject's visit will be based on the actual visit occurring during the treatment duration. These visits will be used to create by visit summaries for laboratory, vital signs, electrocardiograms and other safety analyses data. The end of treatment value is the last non-missing value in the treatment duration.

Any concomitant medication taken within the 14 days after the last dose data will be listed/summarized as part of the concomitant medication listing/table.

AEs for the subject were collected and reported on CRF starting from the time subject signed informed consent to the last visit in the Treatment Phase following subject's last dose. Serious AEs were collected for 28 days after the last dose.

For summaries of safety by time points, the time points will be relative to date of first dose. For standardized reporting, study day windows relative to the first dose (Day 1) in the study will be applied to determine into which week the data will be mapped. Scheduled, unscheduled, and early withdrawal visits will be mapped to weeks. Table 2 below gives the mapping of relative day ranges to week for non-AE safety variables. If a subject did not have a recorded observation falling within a given range of days in order to be assigned to a week, the subject's data for that week will be regarded as missing for summarization purposes. If there are two or more assessments in the same window then:

- if the window is the baseline assessment, then the latest assessment will be used in the summary tables;
- if the window is the follow-up assessment, then the latest assessment will be used in the summary tables;

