### 5.6.2 Adverse Events

The AE verbatim descriptions (investigator terms from the CRF) will be classified into standardized medical terminology using the Medical Dictionary for Regulatory Activities (MedDRA). Adverse events will be coded to the MedDRA (version 18.1 or higher) lower level term (LLT) closest to the verbatim term. The linked MedDRA preferred term (PT) and primary system organ class (SOC) will also be captured in the database.

A TEAE is defined as an AE that:

- Emerges from the date of first dose of study drug in Core Study to 28 days after last end date of dose in prescribed dose entry in Extension Phase, having been absent at pretreatment (Baseline) in Core Study, or
- Reemerges during treatment, having been present at pretreatment (Baseline) in Core Study but stopped before treatment, or
- Worsens in severity during treatment relative to the pretreatment state in Core Study, when the AE is continuous.

Only those AEs that are treatment emergent will be included in summary tables. All AEs, treatment emergent or otherwise, will be presented in subject data listings.

TEAEs will be summarized using the safety analysis set. The incidence of TEAEs will be reported as the number (percentage) of subjects with TEAEs by SOC and PT. A subject will be counted only once within a SOC and PT, even if the subject experienced more than one TEAE within a specific SOC and PT. The number (percentage) of subjects with TEAEs will also be summarized by maximum severity (mild, moderate, or severe).

The number (percentage) of subjects with TEAEs will also be summarized by relationship to study drug (Yes [possibly related, probably related] and No [not related]).

AEs will be analyzed by the actual dose at AE onset.

The number (percentage) of subjects with treatment-related TEAEs will be summarized by SOC and PT. Treatment-related TEAEs include those events considered by the investigator to be related to study treatment.

The number (percentage) of subjects with TEAEs leading to death will be summarized by MedDRA SOC and PT. A subject data listing of all AEs leading to death will be provided.

The number (percentage) of subjects with treatment-emergent SAEs will be summarized by MedDRA SOC and PT. A subject data listing of all SAEs will be provided.

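### The Extension SAP ends the AE treatment period at 14 days in one section but counts TEAEs to 28 days in another, and both SAPs call any on-treatment C-SSRS Yes treatment-emergent without reference to baseline

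*SAP*

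**What the plan says.** **AE window.** Extension SAP 8.2.2 states that, for AEs, the treatment duration begins on Day 1 of the Core Study and "ends 14 days after the last dose of Maintenance Period in Extension Phase". It adds: "The post-treatment duration is considered to begin on the day after the treatment duration for safety". The same section says that AEs were collected from "informed consent to the last visit in the Follow-up following" the last dose.

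Extension SAP 5.6.2 defines a TEAE by three criteria. The first, for new events, carries its own limit: "to 28 days after last end date of dose in prescribed dose entry in Extension Phase". The other two carry no day limit: "Reemerges during treatment, having been present at pretreatment (Baseline) in Core Study but stopped before treatment" and "Worsens in severity during treatment relative to the pretreatment state in Core Study, when the AE is continuous".

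The parallel sentence in Core SAP 8.2.2 says that the AE duration "ends 28 days after the last dose of treatment phase", and Core SAP 5.6.2 also uses 28 days. Protocol 9.5.1.5.1 collects AEs "through the last visit and for 28 days following study drug discontinuation".

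**C-SSRS.** Section 5.6.6 of each SAP sets a C-SSRS window that starts on the first-dose date (the first Core dose in the Extension SAP) and runs through 28 days after the last dose. Any Yes within a category in that window is a treatment-emergent report of behaviour, ideation or suicidality. Baseline enters only through the shift in ideation severity and the by-visit changes in ideation intensity and severity. The proportion with treatment-emergent reports is secondary endpoint 6 in both SAPs.

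**The concern.** TEAE incidence is part of the primary endpoint, and one SAP gives two end dates for the AE period on which it rests. A programmer who takes the general definition from 8.2.2, or who uses it to interpret the two TEAE criteria that state no limit, will produce different counts from one who takes 28 days from 5.6.2.

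The C-SSRS rule has a different fault. It uses the term treatment-emergent but drops the condition that gives the term its meaning. A child whose ideation is at the same level before and after the first dose is counted as having ideation that emerged on perampanel. The trial has no control arm, so comparison with the child's own baseline is the only internal reference for this endpoint.

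**Working it through.** **Step 1. The AE windows side by side.**

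| Source | AE window or collection ends |
|---|---|
| Extension SAP 8.2.2 | last dose + 14 days |
| Extension SAP 5.6.2, new events | last dose + 28 days |
| Extension SAP 5.6.2, re-emerging or worsening events | no day limit stated |
| Core SAP 5.6.2 and 8.2.2 | last dose + 28 days |
| Protocol 9.5.1.5.1, collection | 28 days after discontinuation |

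The 14-day figure is the outlier.

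**Step 2. Size of the gap.** 28 − 14 = 14 days (post-dose days 15 to 28), which is 14/28 = 50% of the tail. Assume a full nominal course of 52 weeks: 52 × 7 = 364 days. The window then ends on Day 364 + 14 = 378 under 8.2.2 and on Day 364 + 28 = 392 under 5.6.2. The disputed days are 14/392 = 3.6% of the longer window. This is a share of calendar days, not of events or children.

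The Extension A Follow-up Visit is due 4 weeks ± 7 days after the last dose (protocol 9.1.3.2), that is on days 28 ± 7 = 21 to 35. It lies wholly outside a 14-day window.

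**Step 3. An AE on post-dose day 20.** If new, it is a TEAE under 5.6.2 and falls in the post-treatment period under 8.2.2. If it re-emerges or worsens on that day, its status depends on where the programmer takes the end of treatment from: 28 days gives a TEAE, 14 days does not.

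**Step 4. The emergence rules compared.**

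| | TEAE (5.6.2, both SAPs) | C-SSRS (5.6.6, both SAPs) |
|---|---|---|
| Absent at baseline, then present | counted | counted |
| Present at baseline, unchanged | not counted | counted |
| Present at baseline, worse | counted | counted |

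Only the middle row differs. For ideation, the shift table would show no worsening for such a child, while the headline proportion counts the child as emergent. For behaviour, no output refers to baseline at all.

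**Step 5. Can a child be positive at baseline?** Exclusion 6 (protocol 9.3.2) removes children with ideation questions 4 or 5 answered Yes within 6 months before Visit 2. Exclusion 5 concerns an unstable psychiatric diagnosis, with significant suicide risk as an example. A child rated 1 to 3 on ideation severity is not barred by the terms of exclusion 6, and is barred by exclusion 5 only if judged to meet it.

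**Step 6. Size.** The documents give no baseline prevalence, so no bias can be computed. Per child only: 1/160 = 0.6 percentage points at the planned N of 160, and 1/65 = 1.5 points at the planned Japanese N of 65. At those sample sizes both are minimums, because the denominator holds only children aged 6 or older.

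**Step 7. The first-dose date.** The C-SSRS window includes it. Footnote a of the visit-mapping tables (Core SAP Table 1, Extension SAP Table 6) classes every assessment on that date as pretreatment. Protocol Table 4 schedules a C-SSRS at Visit 2, Week 0, and protocol 9.5.1.5.7 lists one after dosing on Day 1. Footnote a fits a pre-dose record but not a post-dose one: it would class a true post-dose report as pretreatment. Section 8.2.2 takes the latest value in the baseline window, so that report could become baseline, although 8.2.1 requires baseline to precede the dose.

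**The case against.** On the AE window, the strongest reply is that 5.6.2 defines TEAEs and carries its own 28-day limit, so the TEAE tables follow it, and that no planned output in the Extension SAP is said to use the 14-day period. This largely stands. A reader might infer that TEAEs on days 15 to 28 will be lost from the tables; the documents do not support that for new events. A reader might also infer that re-emerging and worsening AEs are held to 14 days. That is only a possible reading: the 28-day limit opens the definition, and the falls summary in 5.6.2 uses a treatment period running through Follow-up. What remains is a contradiction in the text that leaves a programmer a choice.

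On the C-SSRS, the reply is that the SAP states its rule openly, errs towards over-counting a safety signal, supplies a baseline shift for ideation, and draws on a population already screened for suicide risk. These points limit the harm. They do not correct the headline proportion, and they give behaviour no baseline reference. A reader might also infer that the Visit 2 record is counted both as baseline and as emergent. Footnote a largely answers that for a pre-dose record; the unresolved case is an assessment made after dosing on Day 1.

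Finally, a reader might infer that the 28-day tail in the Core SAP miscounts AEs in children already dosing in Extension A. Core SAP 8.2.2 states the rule for that tail, and the Extension SAP is cumulative from the first Core dose, so no event is lost. It is not part of this point.

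**Conclusion.** Both inconsistencies are in the current text. In the Extension SAP, AEs on post-dose days 15 to 28 are treatment-emergent in 5.6.2 and post-treatment in 8.2.2, with a secondary risk that two of the three TEAE criteria are programmed with the shorter window. The disputed period is 14 days, or 3.6% of a nominal 392-day window if treatment lasts the full 52 weeks; no effect on a result is demonstrated.

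In both SAPs, the C-SSRS secondary endpoint reports persisting ideation or behaviour as emerging on drug. The direction is over-counting. The size is unknown and depends on how many enrolled children aged 6 or older have a Yes at baseline that recurs on treatment. Both matters should be corrected; neither undermines the study.

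**What to change.** 1. In the AE sentence of Extension SAP 8.2.2, change 14 days to 28, so that all three TEAE criteria in 5.6.2 use one window. The separate 14-day sentence on concomitant medication in that section is not part of this change.
2. In section 5.6.6 of both SAPs, define treatment-emergent ideation or behaviour as a report made after the first dose that was absent, or less severe, at the pre-dose baseline. Keep any Yes on treatment as a separate row, without the word emergent.
3. State that a pre-dose record on the first-dose date is baseline only, and that a C-SSRS identified as done after dosing on Day 1 counts as post-dose and is never used as baseline. Reconcile footnote a with protocol 9.5.1.5.7. Do not simply start the window on Day 2: that would discard a true post-dose report and could turn it into baseline.

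The cost is a few sentences and minor reprogramming, including a way to identify any Day 1 post-dose record. The headline C-SSRS proportion becomes less conservative, which the retained row offsets.
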